## 1. Background and Rationale

The study addresses the increasing need for efficient, standardized prenatal health education, especially in light of nursing workforce shortages. Robot-assisted education presents a novel digital solution that may reduce anxiety and enhance health literacy among pregnant women, particularly those diagnosed with gestational diabetes mellitus (GDM).

## 2. Study Objectives

- Primary Objective: To evaluate whether robot-assisted digital education reduces anxiety among pregnant women with GDM.
- Secondary Objectives: To examine the impact on health literacy, satisfaction with health education, and acceptance of digital technologies.

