## 3. Study Design

Type: Randomized Controlled Trial (RCT)

Setting: Obstetrics outpatient clinic of a regional hospital in Taiwan

Duration: November 2023 to January 2024

Groups:

- Experimental group: Robot-assisted education
- Control group: Tablet-based video education

Blinding: Single-blind (participant and assessor)

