## **6. Outcomes**

Primary: Hamilton Anxiety Rating Scale (HAMA)

Secondary: Health Literacy Questionnaire (HLQ), Satisfaction (adapted Black et al.), Technology Acceptance

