## 1. Sample Size Calculation

Using G\*Power with a medium effect size ( $d = 0.5$ ), alpha = 0.05, power = 0.80. Minimum of 64 participants required. Target recruitment: 80 (to allow for dropouts).

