## 3. Analysis Methods

Baseline Characteristics: Independent t-tests or chi-square

Primary Outcome (Anxiety): Independent samples t-test

Secondary Outcomes:

- Health literacy, satisfaction, technology acceptance: t-tests
- Associations: One-way ANOVA and chi-square tests

Software Used: SPSS v25

Missing Data: Excluded from per-protocol; ITT analysis with multiple imputation recommended in future studies

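### Does an objective that names no comparator leave the trial unable to answer its own question when both arms receive device-based education?

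*Protocol*

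**What the plan says.** The Study Objectives section gives the primary aim as "To evaluate whether robot-assisted digital education reduces anxiety among pregnant women with GDM". The secondary aims concern the effect on health literacy, satisfaction with the education and acceptance of technology. None of these sentences names a comparator.

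The next section, Study Design, calls the study a randomised controlled trial and lists two arms: "Experimental group: Robot-assisted education" and "Control group: Tablet-based video education". There is no nurse-led, usual-care or no-education arm.

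The Analysis Methods section fixes the primary comparison as "Primary Outcome (Anxiety): Independent samples t-test" and assigns t-tests to the secondary outcomes.

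The Background and Rationale section places the need for this kind of education in context with the words "especially in light of nursing workforce shortages". It describes the intervention as follows: "Robot-assisted education presents a novel digital solution that may reduce anxiety and enhance health literacy among pregnant women".

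**The concern.** The objective asks whether robot-assisted education reduces anxiety, full stop. The trial randomises between a robot and a tablet video, so its only randomised contrast is the increment of one device-based format over another. If both formats lowered anxiety by the same amount, the between-arm test would be expected to find nothing, although the objective taken literally would be true. A reader could then conclude that the robot does not work.

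In the other direction, the reference to nursing shortages might lead a reader to take a positive result as evidence that the robot can stand in for a nurse, a question no arm addresses. The aim on technology acceptance also looks awkward, because each arm used a different device. At stake would be the meaning of the trial's main conclusion.

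**Working it through.** The question is which effect the protocol sets out to estimate. That is settled by reading its sections side by side.

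| Element | Section | What it fixes |
|---|---|---|
| Aim | Study Objectives | Direction (reduction), outcome (anxiety), population (GDM) |
| Comparator | Study Design | Tablet-based video |
| Outcome measure | Outcomes | HAMA |
| Contrast | Analysis Methods | Two-sample t-test between the arms |
| Within-arm or pre-post effect | None | Not planned anywhere |

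**Step 1: the effect tested.** A two-sample t-test estimates mean HAMA under robot education minus mean HAMA under tablet education. Randomisation makes the two baseline means equal in expectation, so this is also the expected difference in change from baseline. It is a relative effect against the named control.

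**Step 2: what the sample-size figure points to.** The Sample Size Calculation section uses d = 0.5 and states "alpha = 0.05, power = 0.80. Minimum of 64 participants required". Testing is two-sided.

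- Two-sample test, normal approximation: 2 × (1.960 + 0.842)² / 0.5² = 2 × 7.85 / 0.25 ≈ 62.8, so 63 per arm.
- Two-sample test, exact noncentral t: 63.77, so 64 per arm (128 in total).
- Paired or one-sample test of a within-arm change, exact: 33.37, so 34.

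The figure 64 matches the between-arm calculation, taken as a per-arm number, and not the within-arm one. The protocol does not say which test was selected in the software, so this is an inference, but it agrees with Step 1. That 64 is written as though it were the total is a separate matter, on which this point does not depend.

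**Step 3: the equal-improvement scenario.** Suppose both arms fall by 0.5 SD, an illustrative value not taken from the protocol. The expected difference is −0.5 − (−0.5) = 0, and the chance of a non-significant two-sided 5% test is 1 − 0.05 = 0.95. The same 0.95 follows for any common fall, including none. The figure restates the significance level and measures no defect in this plan.

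**Step 4: the supposed wrong conclusion.** For the harm to come from the plan, the protocol would have to say that a null result means the robot does not lower anxiety. It contains no rule for interpreting a null result and no pre-written conclusion.

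**Step 5: nurse-led education.** The workforce shortage appears only as background. Neither the rationale nor the objectives state that the robot will be compared with nurses, shown equivalent to them or used to replace them. The trial cannot be faulted for not testing a claim it does not make. A screen-based active control is also a reasonable choice, because it helps separate the effect of the robot from that of receiving material on a device.

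**Step 6: technology acceptance.** This aim is about impact, not absolute reduction. Acceptance can be scored and compared in both arms, and the device is the randomised factor. Whether the items refer to comparable objects in the two arms is a different, measurement question. It would need the questionnaire, which the protocol does not reproduce.

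**The case for a change.** The strongest case for the concern is that an objective is the protocol's own statement of its question and should not have to be assembled from three sections. A null result is also far from unlikely. Assuming 1:1 allocation (the ratio is not stated), the recruitment target of 80 gives 40 per arm and about 60% power at d = 0.5. Over an assumed range of smaller differences, power falls to 42% at d = 0.4, 26% at 0.3 and 14% at 0.2. The protocol calls d = 0.5 only a medium effect and does not tie it to an active tablet control. On this view, the plan ought to say in advance what a null result would mean.

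Part of this stands. The objective does omit the comparator, the only randomised contrast is robot against tablet video, and any conclusion is bounded by that contrast. Adding the comparator would be good drafting.

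The rest does not carry the concern. The sections to be joined include the one that follows immediately, and they agree with one another. The power figures bear on the sample size, not on whether the objective and the analysis match. Possible over-reading is a matter for the eventual report, and nothing in the protocol commits the sponsor to it.

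**Conclusion.** The concern does not hold. The objective is brief, but the design and analysis sections complete it consistently: the question is whether robot-assisted education lowers HAMA relative to tablet-based video, and that is what the primary test addresses. No section states an absolute effect, contradicts the named comparator or misdirects the analysis. Rewording the objective would alter no arm, participant, measurement, test or result, so the effect on the trial is nil and what remains is a preference about wording.

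This rests on giving the verb its ordinary meaning in a controlled trial, and on the absence of any planned within-arm analysis or null-result rule in the protocol. It does not endorse the sample size, and it does not extend the trial's conclusions to nurse-led education or to no education.

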## 3. Study Design

Type: Randomized Controlled Trial (RCT)

Setting: Obstetrics outpatient clinic of a regional hospital in Taiwan

Duration: November 2023 to January 2024

Groups:

- Experimental group: Robot-assisted education
- Control group: Tablet-based video education

Blinding: Single-blind (participant and assessor)

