## **5. Intervention**

A 30-minute robot-assisted session on GDM information using visual, audio, and interactive storytelling features.

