## 2. Randomization

Block randomization via computer-generated sequence. Allocation concealed until participant assignment.

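### The protocol lists participants as blinded, but women taught by a robot or by a tablet video cannot be blind to the device they receive

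*Protocol*

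**What the plan says.** The Study Design section (section 3) gives one line on masking: "Blinding: Single-blind (participant and assessor". It lists the arms as "Experimental group: Robot-assisted education" and "Control group: Tablet-based video education". The Intervention section (section 5) describes the experimental session: "A 30-minute robot-assisted session on GDM information using visual, audio, and interactive storytelling features".

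The Randomization section says "Allocation concealed until participant assignment". This is the only other statement about who knows the allocation, and when.

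The Study Objectives section (section 2) includes "satisfaction with health education, and acceptance of digital technologies" among the secondary objectives. The Outcomes section (section 6) lists both as secondary outcomes, and the Analysis Methods section compares them between groups: "Health literacy, satisfaction, technology acceptance: t-tests".

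**The concern.** The blinding line names the participant as a blinded party. The arms differ in a physical device that each woman has in front of her during her session, so the design lacks a property that the protocol says it has. The line is also inconsistent in itself, since single-blind is followed by two blinded parties.

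At stake is what may be claimed from the results. Participant blinding tells a reader that answers given by participants were not shaped by knowing the allocation. Satisfaction with the education and acceptance of the technology are the outcomes where that assurance would be relied on most directly, because they record what women think of what they received. Anyone who takes the line at face value would credit those comparisons with a protection that they do not have.

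**Working it through.** There is no figure to reproduce, so the check sets the statements side by side.

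1. **What is claimed.** The blinding line names participant and assessor. It does not say what the participant is unaware of. The ordinary reading is the allocation.

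2. **What separates the arms.** Allocation decides whether a woman is taught by a robot or by a tablet video. The device is itself the allocated treatment, so a woman who knows her device knows what she was allocated, even if she does not know that an alternative existed.

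3. **Whether the device could be hidden.** The robot session is visual, audible and interactive. The protocol describes no sham or masking of the device. With these two arms, it is hard to see what such a procedure could be: a woman who interacts with a robot for 30 minutes cannot be unaware of it, and the same holds for one who watches a video on a tablet.

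4. **Whether another statement rescues the claim.** Concealment until assignment protects against selection at enrolment. It ends when the woman is assigned, and so does not bear on what she knows during the session or when she answers questions afterwards. The concealment statement itself is not in question.

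5. **Whether a narrower meaning is possible.** Both arms are digital education. Women may have been kept unaware of the study hypothesis or of the other arm. That would be a real procedure, but it is not blinding to the device, and the protocol does not state it.

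6. **The label.** Two parties are named: participant and assessor. Single-blind describes one. If participant blinding is withdrawn, at most the assessor remains, and the label should follow whatever was actually done.

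7. **Which outcomes are affected on the document's own terms.** Satisfaction with health education and acceptance of digital technologies are, by what they are named to measure, the woman's view of what she received or used. Both are tested between groups. This identifies where the interpretation changes and does not measure any bias.

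**The case against.** The strongest reply is that participant blinding may have been meant in the narrower sense, as unawareness of the hypothesis or of the other arm. The protocol does not say what participants are blinded to. What women were told would be in the consent material, which is not part of the text reviewed, so silence on this is not evidence against it. This stands in part. The narrower procedure may have been used, and the fix must leave room for it. It does not rescue the line as written, because unawareness of that kind is not blinding to allocation when the device is the allocation.

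A second reply is that satisfaction with an education session and acceptance of a technology can be judged only by someone who knows what she used, so no blinded version of these measures exists. That is also fair. It means that the design is not at fault for leaving these outcomes unblinded. The fault lies in a statement suggesting that they are blinded.

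Three stronger readings are tempting, and the document does not support them:

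- **That the anxiety result is biased because participants know their device.** The Outcomes section says only "Primary: Hamilton Anxiety Rating Scale (HAMA". It does not describe who scores the scale or how, so any argument about how knowledge of the device enters the score would rest on information from outside the protocol.
- **That the assessor is not blinded either.** Nothing in the document shows this. The rater and the mode of administration are details that may be recorded elsewhere, and their absence here is no finding.
- **That the two affected outcomes show how large the bias is.** Counting outcomes gives the scope of a wording correction. It says nothing about error rate, estimate or power. Both arms are digital, and the robot's appeal may be part of the effect that the trial sets out to test, so a difference on these outcomes need not be bias at all.

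**Conclusion.** The point holds as a misstatement of the design. Participants cannot be blinded to the device they receive, and single-blind does not fit the two parties named. The conclusion follows from the description of the arms and of the robot session. It assumes only that a woman notices whether a robot or a tablet is teaching her.

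The consequence is limited to interpretation. Group differences in satisfaction and technology acceptance should be read as opinions of participants who know their device, with no claim of protection by participant blinding. No size of bias is derivable and none is asserted. No conclusion is drawn about how HAMA was scored or about assessor blinding. The randomised comparison itself is not called into question.

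**What to change.** Correct the blinding line in the Study Design section:

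- Remove the claim that participants are blinded to allocation, and state that they know which device they receive.
- If women were kept unaware of the hypothesis or of the other arm, say that in those terms. State it only if it was actually done.
- Make the blinding label match the parties actually blinded.
- When reporting satisfaction and technology acceptance, describe group differences as opinions of participants who know their device.

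The cost is a wording change, once the sponsor has confirmed what participants were told and which parties were in fact blinded. Tests, endpoints, sample size and procedures stay as they are. The downside is that the stated design will look less rigorous than the current line suggests.

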## 4. Participants

Inclusion Criteria:

- Pregnant women aged  $\geq 21$
- GDM diagnosis
- Taiwanese nationality

Exclusion Criteria:

- Chronic illness
- Cognitive impairment or language barrier

## **5. Intervention**

A 30-minute robot-assisted session on GDM information using visual, audio, and interactive storytelling features.

## **6. Outcomes**

Primary: Hamilton Anxiety Rating Scale (HAMA)

Secondary: Health Literacy Questionnaire (HLQ), Satisfaction (adapted Black et al.), Technology Acceptance

## **7. Ethics**

Approved by the Institutional Review Board of Taipei Medical University. Informed consent obtained (ethical approval number N202309040).

## **8. Data Availability**

Available upon reasonable request to the corresponding author.

## 1. Sample Size Calculation

Using G\*Power with a medium effect size ( $d = 0.5$ ), alpha = 0.05, power = 0.80. Minimum of 64 participants required. Target recruitment: 80 (to allow for dropouts).

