## 4. Significance Level

Two-tailed tests with  $\alpha = 0.05$ .

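### The minimum of 64 participants is the per-group number for d = 0.5, not the trial total; a trial of 80 has about 50–60% power, not 80%

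*Protocol*

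**What the plan says.** The sample size section (Protocol, 1. Sample Size Calculation) names G*Power as the tool and gives the inputs as a "medium effect size ( $d = 0.5") with "alpha = 0.05, power = 0.80". Its result is: "Minimum of 64 participants required. Target recruitment: 80 (to allow for dropouts"). Neither number is marked as per group.

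The rest of the design comes from other sections:

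- Section 3, Study Design, lists two parallel groups: "Experimental group: Robot-assisted education" and "Control group: Tablet-based video education".
- Section 3, Analysis Methods, fixes the primary test: "Primary Outcome (Anxiety): Independent samples t-test".
- Section 4, Significance Level, sets the sidedness: "Two-tailed tests with" alpha = 0.05.
- Section 2, Randomization, says "Block randomization via computer-generated sequence" and gives no allocation ratio.

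**The concern.** For a standardised difference of 0.5, a two-sided 5% test and 80% power, 64 is the familiar number for one arm of a two-arm comparison. Here it appears as the number of participants the trial requires, and the recruitment target of 80 is built on it. That points to a per-group output being carried forward as the trial total.

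If so, the trial is half the size its own assumptions call for. The primary objective is to find out whether robot-assisted education reduces anxiety, measured by HAMA, in a comparison with tablet video. A reader who accepts the stated 80% power would think that a true effect of d = 0.5 is missed one time in five. If it is really missed four or five times in ten, a non-significant result says little about whether the robot helps.

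**Working it through.** **Inputs**

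| Input | Value | Source |
|---|---|---|
| Effect size | d = 0.5 | 1. Sample Size Calculation |
| Alpha | 0.05 | 1. Sample Size Calculation; 4. Significance Level |
| Sides | two | 4. Significance Level |
| Power | 0.80 | 1. Sample Size Calculation |
| Test | independent-samples t-test, unadjusted | 3. Analysis Methods |
| Groups | two | 3. Study Design |
| Allocation | 1:1 | assumption; not stated |

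**Step 1. Reproduce the figure of 64**

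The normal approximation for n per group is

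n = 2 × (z₀.₉₇₅ + z₀.₈₀)² / d² = 2 × (1.960 + 0.842)² / 0.25 = 62.8, so 63 per group.

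The exact calculation uses the noncentral t distribution with 2n − 2 degrees of freedom and noncentrality d × √(n/2). It gives n = 63.77, so 64 per group and **128 in total**. At n = 64 the noncentrality is 0.5 × √32 = 2.83, and power is 0.801. So 64 is reproduced exactly, but as the size of one group.

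**Step 2. Could 64 be a total under another test?**

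| Test at d = 0.5, power 0.80 | Participants needed in total |
|---|---|
| Independent t-test, two-sided | 128 (64 per group) |
| Independent t-test, one-sided | 102 (51 per group) |
| Paired or one-sample t-test, two-sided | 34 |
| Paired or one-sample t-test, one-sided | 27 |

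None of these gives 64 as a total. The plan's own sections on analysis methods and significance level rule out all but the first.

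**Step 3. Power with the stated numbers as totals**

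Two-sided, d = 0.5, equal groups, noncentral t:

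| Analysed | Per group | Noncentrality 0.5 × √(n/2) | Power |
|---|---|---|---|
| 64 | 32 | 0.5 × √16 = 2.00 | 0.504 |
| 72 | 36 | 0.5 × √18 = 2.12 | 0.553 |
| 80 | 40 | 0.5 × √20 = 2.24 | 0.598 |
| 128 | 64 | 0.5 × √32 = 2.83 | 0.801 |

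The type II error is 1 − 0.598 = 0.40 with 80 analysed and 1 − 0.504 = 0.50 with 64. Equal allocation is the favourable case: a 27/53 split of 80 gives power 0.55. Even a one-sided test, which the plan excludes, would reach only 0.63 with 64 and 0.72 with 80.

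**Step 4. Detectable effect at 80% power**

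Solving the same power function for d gives 0.71 with 64 analysed and 0.63 with 80.

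**Step 5. Recruitment implied by the stated inputs**

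The plan gives no dropout rate. Its two figures imply 1 − 64/80 = 20%. At that loss, 128 evaluable participants need 128 / 0.80 = 160 recruited.

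**The case against.** The strongest reply is that the section says neither total nor per group. The inputs give exactly 64 per group, so the calculation may be sound with only a label left out. The trial would then have 128 evaluable and 160 recruited, with power 0.801 at 64 per group and 0.882 at 80 per group. This cannot be strictly excluded. But a required number of participants and a recruitment target, given without qualification, ordinarily describe the whole trial, and nothing else in the document points to 160. Even on this reading the section misstates the trial's size by a factor of two and needs correcting.

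Three lesser points:

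- **The 50% end is the pessimistic end.** It applies only if the analysed number falls to 64. No dropout rate is given, and the intervention is a single 30-minute session. This is fair: with everyone analysed the figure is about 60%. However, 64 is the plan's own stated minimum, and the plan says missing data are excluded and leaves multiple imputation to future studies, so losses would reduce the analysed number.
- **Baseline adjustment could recover power.** Adjustment multiplies the required size by about 1 − r², so 64 in total would suffice only if 1 − r² = 64/128, that is r = √0.5 ≈ 0.71 between baseline and outcome. The planned analysis is an unadjusted t-test and no correlation is given.
- **Neither the treatment estimate nor the type I error is biased.** This is true. The damage is to the stated power and to what a null result can mean.

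**Conclusion.** The concern holds. On the plan's own inputs, 64 is the requirement for each group and 128 for the trial. Read as written, a recruitment of 80 gives between 50.4% power (64 analysed) and 59.8% power (80 analysed) for d = 0.5, against the stated 80%.

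This rests on two assumptions: that 64 and 80 are trial totals, which is the plain reading, and that allocation is 1:1, which is the more favourable choice for the trial. The figure of 160 also depends on a 20% loss inferred from 64 out of 80. Because the error is a factor of two in the number behind the primary comparison, it must be corrected.

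**What to change.** State the result of the calculation as 64 per group and 128 evaluable in total, together with the allocation ratio and the assumed dropout rate. Then take whichever of these matches the trial:

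- **80 is the trial total and stays so.** Replace the 80% claim with about 60% power for d = 0.5 if all 80 are analysed and about 50% if 64 are. Alternatively, state that 80% power is available only for d of about 0.63 (80 analysed) to 0.71 (64 analysed). Report the difference in HAMA with its 95% confidence interval, and do not interpret a non-significant result as no effect.
- **64 and 80 were meant per group.** Say so explicitly: 128 evaluable and 160 recruited.

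Either is a change of wording and numbers. The first makes the stated power less favourable but needs no added participants. Actually delivering 80% power for d = 0.5 would need 128 evaluable, or 160 recruited at a 20% loss, which is 80 more than a total target of 80.
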